5.1.5 Confirmation of complete PVI

Electrical isolation of a PV is demonstrated by entrance and exit block. Entrance block is defined as the absence of local potentials inside the vein as assessed by the POLARMAP™ circular mapping catheter. Exit block is defined as absence of atrial capture while pacing from inside the vein with the POLARMAP™ circular mapping catheter. If a PV shows reconnection, repeat cryoablation will be performed with the goal of achieving electrical isolation. This can be performed with the 28 mm or 31 mm balloon size per operator discretion. Complete PVI is defined as electrical isolation of all PVs. After complete PVI, post-ablation UHDx mapping will be performed.

5.1.6 Post-ablation UHDx mapping

After achieving complete PVI, the 64-pole mini-basket mapping catheter will be introduced through the POLARSHEATH for repeat mapping. Repeat mapping will be preferentially performed in sinus rhythm with prior cardioversion of AF if required. There will be no specified waiting time before remapping. LA voltage maps will be constructed with special point density in the antra of PVs. Post-ablation LA lesion surface area will be assessed as previously described.²³ The key parameters that will be collected are described in the Methods section. If conduction gaps or PV reconnections are found during UHDx mapping, the mapping catheter will be replaced by the POLARx™ cryoablation catheter and additional ablations will be performed to achieve complete PVI. Another UHDx map will be constructed after re-isolation.

5.1.7 Follow-up after index procedure

The day following the procedure, the groin will be inspected for groin hematoma and a transthoracic echocardiogram will be performed to rule out pericardial effusion. Patients will be scheduled for an outpatient visit 3, 6 and 12 months after the index procedure.

This follow-up schedule is standard of care in the Erasmus MC after a PVI. During these visits a physical examination, 12-lead ECG and Holter will be performed. If a PNP occurred during the index procedure, a chest X-ray will be performed during the outpatient clinic visit. The indication for a repeat AF ablation is according to the discretion of the treating physician. During a repeat ablation it is preferable to perform a bipolar voltage map to gain insight in the durability of the antral lesion size area.

5.1.8 Data collection schedule

Procedure	Enrollment (up to day -60)	Baseline (up to day -60)	Index procedure (day 0)	Month 3 follow-up (91±14 days)	Month 6 follow-up (180±30 days)	Month 12 follow-up (365±30 days)	Unscheduled visit
Informed consent	X						
Eligibility criteria	X	X	X				
Demographics		X					
Medical history		X					
Physical examination		X		X	X	X	X
PV anatomical assessment (CT)		X					
TTE		X					
Screening for LA thrombus			X				
Procedural data			X				
12-lead ECG		X	X	X	X	X	X
PNP assessment			X	(X) ¹	(X) ¹	(X) ¹	
Holter monitor				X	X	X	X
Documentation of repeat ablation				X	X	X	
Medications	Prior and current antiarrhythmic medications and anticoagulant therapy regimen from enrollment through end of visit study						
Protocol deviations	From enrollment through end of visit study						
Adverse event assessment	Continuous from enrollment through end of visit study						

¹ Assessment of follow-up visit is only applicable for subjects who had phrenic nerve palsy detected at the index procedure.

5.2 Use of co-intervention (if applicable)

N/A

5.3 Escape medication (if applicable)

N/A

6. INVESTIGATIONAL PRODUCT

6.1 Name and description of investigational product

The POLARx™ FIT cryoablation catheter is CE-marked and is indicated for the treatment of patients with symptomatic AF. In comparison to the previous generation of POLARx™ cryoablation catheter, the POLARx™ FIT cryoablation catheter can apply cryoablation treatment with either 28 mm or 31 mm balloon size per operator discretion. The POLARx™ FIT catheter will expand to the standard balloon size of 28 mm upon every inflation. After each inflation and prior to initiating ablation, the user can increase the balloon size using the console user interface. The larger size is enabled by increasing the inner balloon pressure from 2.5 psi to 7.5 psi. To ensure the freezing capability of the larger size balloon is consistent with the standard size balloon, the nitrous oxide flow rate during ablation is increased from 7800 sccm to 8700 sccm. All other aspects of the nitrous oxide delivery and control for POLARx™ FIT are unchanged from POLARx™. A detailed overview of the hardware components and connections of the POLARx™ FIT cryoablation system is provided in Figures 6.1.1. and 6.1.2. The individual devices within the cryoablation system and their UPN are listed in Table 6.1.1.

Figure 6.1.1. POLARx™ FIT cryoballoon

[figure not shown]
[figure not shown]

Figure 6.1.2. Overview of all connections of the POLARx™ FIT cryoablation system**Table 6.1.1.** Cryoablation devices used in the **BETTER-FIT** study

Product name	Product description	UPN
POLARx ST	POLARx Balloon Catheter ST 28mm	M004CRBS2000
POLARx LT	POLARx Balloon Catheter LT 28mm	M004CRBS2100
POLARSHEATH™	POLARSHEATH Steerable Sheath	M004CRBS3050
POLARMAP™	POLARMAP Mapping Catheter 20mm	M004CRBS7200
SMARTFREEZE™	SMARTFREEZE Cryo Console	M004CRBS4000
DMS Sensor	Diaphragm Movement Sensor	M004CRBS6110
Cryo Extension Cable	SMARTFREEZE Electrical Ext Cable	M004CRBS5100
Cryo Cable	Cryo Gas Cable	M004CRBS5200
POLARMAP EGM Pin Breakout Cable	POLARMAP EGM Pin Breakout Cable	M004CRBS6200
Interconnection Box	Interconnection Box	M004CRBS4110
Dual Foot Pedal Switch	Foot Switch	M004CRBS4200

[figure not shown]
6.2 Summary of findings from non-clinical studies

The *Instructions For Use* (IFU) of the POLARx™ FIT cryoablation catheter is attached as supplement material. Because the device is CE marked, available on the market and the device is used within its indications, we have not requested a new IB for this study.

6.3 Summary of findings from clinical studies

FROZEN-AF (NCT 041331680) was a multi-center, open label, prospective, single arm study to document the safety and performance of Boston Scientific's Cryoablation System (IDE trial) which started in June 2020. As a substudy, the efficacy and safety of the POLARx™ FIT cryoablation catheter was evaluated in 50 patients.²⁰ Acute isolation was achieved in all 50 patients. The novel 31 mm configuration was used in 65% of ablations. In the 198 ablations performed at 31mm, 80.8% achieved a grade 4 occlusion. In PVs where the first ablation was performed at 31mm the single shot isolation rate was significantly higher than in PVs where the first ablation was performed at 28mm (62.1% versus 35.3%). Notably, there was only 1 instance of transient phrenic nerve paralysis which resolved prior to discharge. Preliminary landmark-based analysis of a subset of veins suggests that inflation to 31mm results in a marked antral shift of balloon position.

Figure 6.3.1. Antral shift of balloon position.²⁰

6.4 Summary of known and potential risks and benefits

Cryoballoon ablation is a safe and effective tool for the treatment of AF with a high rate of durable PVI. A recent large Netherlands Heart Registration (n=13,823) demonstrated that CB ablation was associated with less cardiac tamponades (0.3% versus 0.8%) and less vascular complications (1.3% versus 1.7%) compared to radiofrequency ablation.²⁵ In contrast, CB ablation was associated with a higher risk of phrenic nerve palsy (1.5% versus 0.1%). These data are mainly based on the use of the second-generation CB (Arctic Front Advance).

There is limited data on the incidence of periprocedural complications when using the POLARx™ cryoablation catheter. Studies have shown that the risk of PNP is similar

to Arctic Front Advance Pro™.⁸ Real-world data from 372 patients in the POLAR-ICE registry (NCT 04250714) have demonstrated the following complications (Table 9.4.1.). It is expected that the POLARx™ FIT cryoablation catheter will have a similar safety profile as the POLARx™ cryoablation catheter. As can be appreciated from Table 6.4.1., most complications are related to the procedure and not the device itself.

Table 6.4.1. Periprocedural complications in the POLAR-ICE registry (n=388)

Complication	Number of patients (%)
Phrenic nerve palsy	9 (2.3%)
Serious vascular access complications	6 (1.5%)
Cardiac tamponade	2 (0.5%)
Air embolism	2 (0.5%)
Persistent gastroparesis	1 (0.3%)
Myocardial infarction	1 (0.3%)
Stroke	1 (0.3%)

Abstract at EHRA 2022, Tilz et al.

6.5 Description and justification of route of administration and dosage

N/A

6.6 Dosages, dosage modifications and method of administration

N/A

6.7 Preparation and labelling of Investigational Medicinal Product

N/A

6.8 Drug accountability

N/A

7. NON-INVESTIGATIONAL PRODUCT

N/A. The study doesn't include a non-investigational product.

- 7.1 Name and description of non-investigational product(s)**
- 7.2 Summary of findings from non-clinical studies**
- 7.3 Summary of findings from clinical studies**
- 7.4 Summary of known and potential risks and benefits**
- 7.5 Description and justification of route of administration and dosage**
- 7.6 Dosages, dosage modifications and method of administration**
- 7.7 Preparation and labelling of Non Investigational Medicinal Product**
- 7.8 Drug accountability**

8. METHODS

8.1 Study parameters/endpoints

8.1.1 Main study parameter/endpoint

- Extent of antral lesion size (continuous variable) directly after cryoablation with a 31 mm balloon size POLARx™ FIT cryoablation catheter. Measures of antral lesion size are described in paragraph 8.3.1. and Table 8.3.1.1.

8.1.2 Secondary study parameters/endpoints (if applicable)

- Proportion of grade 4 occlusion (continuous variable, expressed as %) with a 31 mm balloon size POLARx™ FIT cryoablation catheter (on PV level) during cryoballoon procedure.
- Single shot success rate (continuous variable, expressed as %) with a 31 mm balloon size POLARx™ FIT cryoablation catheter (on PV level) during cryoballoon procedure.
- Difference in proportion of grade 4 occlusion with a 28 mm or 31 mm balloon size (continuous variable, expressed as %) POLARx™ FIT cryoablation catheter (on PV level) during cryoballoon procedure.

8.1.3 Other study parameters (if applicable)

The cumulative 1-year freedom from atrial arrhythmias after cryoballoon ablation will be described using Kaplan-Meier method using a blanking period of 3 months.

8.2 Randomisation, blinding, and treatment allocation

N/A

8.3 Study procedures

8.3.1 Assessment of antral lesion size

In the pre- and post-ablation UHDx-map, bipolar voltage will be assess using a scar-cutoff <0.3 mV.²³ The following spatial measurements will be made consistent with a previously published method by Gunawardene et al.²³: (1) the surface areas of the posterior left- and right-sided PV antral isolation, (2) the LAPW surface area with voltage pre- and post-ablation, and (3) the distance between the ipsilateral, antral levels of isolation at superior, middle and inferior latitudes of the LAPW (Figures 8.3.1.A,B and D). The surface area of each PV ostium and the area of the circular antral ablation lesion was measured around each ipsilateral PV pair (Figure

8.3.1.C). Low-voltage areas will be quantified using a bipolar voltage <0.3 mV. The scale on the maps will be set from 0.1 to 0.3 mV. The purple region represents unablated tissue with a bipolar voltage >0.3 mV. The scar-border zone will be represented by bipolar voltages between 0.1-0.3 mV. The PV ostium is located by the steep angle between the LA wall and the tubular aspect of the PV.

Figure 8.3.1. Methods for measurements of surface areas and distances in pre- and postablation UHDx maps. (A) Pre-ablation UHDx voltage map and measurement of LAPW surface area (indicated by the white dots) and pre-ablation superior, middle, and inferior line. (B) Postablation UHDx voltage map and measurement of the non-ablated LAPW surface area (indicated by the white dots) and postablation superior, middle, and inferior line. (C) Measurement of the PV ostia sizes of the LSPV and LIPV and the area of the circumferential antral ablation along the ipsilateral lateral PV pair (indicated by the white dots). (D) Measurements of the posterior surface areas of the left- and right-sided pulmonary vein antral isolation areas. Modified from Gunawardene et al.²³

[figure not shown]

Table 8.3.1.1. provides an overview of the key parameters assessing the extent of the antral lesion size.

Table 8.3.1.1. UHDx measurements

Measurement	Preablation	Postablation
Nonabladed LAPW surface area (cm ²)	X	X
Superior line (mm)	X	X
Middle line (mm)	X	X
Inferior line (mm)	X	X
Total LPV ostia (cm ²)	-	X
- LSPV ostia (cm ²)		
- LIPV ostia (cm ²)		
- LCV ostia (cm ²), if applicable		
Total RPV ostia (cm ²)	-	X
- RSPV ostia (cm ²)		
- RIPV ostia (cm ²)		
- RCV ostia (cm ²), if applicable		
Left-sided circumferential antral lesion area (cm ²)	-	X
Right-sided circumferential antral lesion area (cm ²)	-	X
Posterior PV antral isolation area	-	X
- LSPV (cm ²)		
- LIPV (cm ²)		
- RSPV (cm ²)		
- RIPV (cm ²)		
- LCV (cm ²), if applicable		
- RCV (cm ²), if applicable		

Abbreviations: LAPW, left atrial posterior wall; LCV, left common pulmonary vein; LIPV, left inferior pulmonary vein; LPV, left pulmonary vein; LSPV, left superior pulmonary vein; RCV, right common pulmonary vein; RIPV, right inferior pulmonary vein; RPV, right pulmonary vein; RSPV, right superior pulmonary vein.

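### The circumferential and posterior antral areas have no pre-ablation reading, so existing low voltage can be credited to the balloon and section 10.1's percentage change cannot be computed for them

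*Combined protocol and SAP*

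**What the plan says.** The primary endpoint in section 8.1.1 is "Extent of antral lesion size (continuous variable) directly after cryoablation with a 31 mm balloon size POLARx™ FIT cryoablation catheter". It refers to section 8.3.1 and Table 8.3.1.1 for the measures, so it is a set of measures and not one area.

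Section 8.3.1 reads both maps with the same threshold: "In the pre- and post-ablation UHDx-map, bipolar voltage will be assess using a scar-cutoff <0.3 mV". It quantifies low voltage by that rule ("Low-voltage areas will be quantified using a bipolar voltage <0.3 mV") and explains the display: "The purple region represents unablated tissue with a bipolar voltage >0.3 mV". By implication, tissue below 0.3 mV on the post-ablation map is read as ablated.

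Table 8.3.1.1 treats two groups of measures differently:

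- The nonablated posterior wall area and the superior, middle and inferior lines are marked for both maps. This matches the text, which asks for "the LAPW surface area with voltage pre- and post-ablation".
- "Left-sided circumferential antral lesion area", "Right-sided circumferential antral lesion area" and "Posterior PV antral isolation area" have a dash before ablation and a cross after it.

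Section 10.1 names six absolute measures: nonablated posterior wall, three lines, circumferential area and posterior antral area. It then defines relative measures as the percentage difference between the two maps for the absolute measures, with none excepted.

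**The concern.** The protocol has a baseline for the measures of what remains (posterior wall and lines) but none for the measures of the lesion itself. If part of the antrum was below 0.3 mV before the first freeze and lies at or inside the traced border, nothing in section 8.3.1 or 10.1 keeps it from being counted as balloon effect. Eligibility (sections 4.2 and 4.3) has no low-voltage criterion.

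An error of this kind can only enlarge the area, which is the direction of the hypothesis in the Summary and section 11.4. There is one arm, so no comparator cancels it, and more patients would not reduce it. The circumferential areas are also the only quantities that section 4.4 uses to justify 20 patients.

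The second issue does not depend on how much low voltage exists: section 10.1 asks for a pre-to-post change in areas for which the table collects no pre-ablation value.

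**Working it through.** **The plan's own figure.** Section 4.4 gives N = 20 with no target precision or formula, so N itself cannot be reproduced. Its side figures can: 20 × 4 = 80 veins; 20/8 = 2.5 patients per month; 20/(100 × 8/12) = 30% of the target population.

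**Inputs.** From section 4.4: n = 20; left area 20.5 ± 3.8 cm²; right area 25.5 ± 5.7 cm². These come from a cited pulsed field ablation study, so results in cm² are illustrative. Assumption: f, the share of the measured area already below 0.3 mV before ablation. The documents give no value, so a range is shown.

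**Precision implied by N = 20.** Half-width = t(0.975, 19) × SD/√n, with t = 2.093.

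- Left: 2.093 × 3.8/√20 = 2.093 × 0.850 = 1.78 cm², interval 18.72 to 22.28.
- Right: 2.093 × 5.7/√20 = 2.093 × 1.275 = 2.67 cm², interval 22.83 to 28.17.

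**Overstatement.** Bias = f × mean area, taking all of f as wrongly attributed (the worst case for a given f). Coverage of a nominal 95% interval comes from the noncentral t with 19 degrees of freedom and noncentrality bias/SE.

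| Assumed f | Left bias (cm²) | Left coverage | Right bias (cm²) | Right coverage |
|---|---|---|---|---|
| 1% | 0.21 | 94% | 0.26 | 95% |
| 2% | 0.41 | 93% | 0.51 | 93% |
| 5% | 1.03 | 79% | 1.28 | 84% |
| 10% | 2.05 | 37% | 2.55 | 52% |
| 20% | 4.10 | 0.5% | 5.10 | 3% |

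The bias equals the half-width at f = 1.78/20.5 = 8.7% on the left and 2.67/25.5 = 10.5% on the right. Section 4.4 gives no planning value for the posterior antral area, so no size can be computed for it.

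**Section 10.1 against Table 8.3.1.1.** Of the six absolute measures, four (posterior wall and three lines) have both readings, so their percentage change can be computed. Two (circumferential and posterior antral areas) have only the post-ablation reading, so theirs cannot.

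Adding a baseline low-voltage reading would not make a percentage useful for these two. With baseline f × A and post-ablation A, the change is (1 − f)/f: 1,900% at f = 5%, 4,900% at f = 2%, and undefined at f = 0. A difference in cm² avoids this.

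**The case against.** The strongest reply has four parts.

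1. **Nothing shows that baseline low voltage is present.** Patients have paroxysmal AF. Previous left atrial ablation, previous cardiac surgery, moderate or severe valve disease, ejection fraction below 45% and LA diameter above 55 mm are all excluded. This may keep the share small, and at 2% or less the effect is negligible. The point stands as a limit on size; the documents do not settle the share either way.

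2. **The tracing rule cannot be checked.** Figure 8.3.1 is not shown and the published method is not available here. Whether separate low-voltage patches enter the contour is unknown. This also stands: the overstatement is possible, not demonstrated.

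3. **Subtraction could create the opposite error.** Tissue that was below 0.3 mV and was then frozen or isolated belongs to the lesion or isolated antrum. Removing all of it would bias the area downward and change what is estimated, especially for a measure defined as an isolation area. This stands, and it rules out replacing the reported area with a subtracted one.

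4. **The consequence is limited.** The primary analysis is descriptive, with no test of lesion size and no 28 mm lesion comparator, and several primary measures do have a baseline. This is true, but the circumferential areas carry the sample size argument, and a descriptive estimate is still meant to describe the balloon's effect.

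A reader might infer that the primary result is biased upward as a matter of fact. The documents do not support that: there is no single primary area, the posterior wall area and lines are read on both maps, and neither the presence nor the amount of baseline low voltage is given.

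**Conclusion.** Two things follow from the text. First, the circumferential and posterior antral areas come from the post-ablation map alone, with no rule for tissue already below 0.3 mV, so these primary measures can be overstated; if there is an error of this kind, it is upward. Second, section 10.1 and Table 8.3.1.1 conflict, because the percentage change cannot be computed for these areas from what the table collects. The second holds whatever the baseline voltage.

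The size of the first is open. It is negligible at a share of 2% or less, material from about 5%, and as large as the sampling uncertainty at 8.7% (left) and 10.5% (right). These figures rest on planning values from another technique and treat the whole share as wrongly attributed. The pre-ablation maps, acquired in any case, would show which situation applies.

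**What to change.** In section 8.3.1 and Table 8.3.1.1:

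- Transfer the post-ablation border to the patient's pre-ablation map and measure, on each side, the area inside it already below 0.3 mV.
- Keep the unsubtracted area as the reported lesion or isolation area, so that comparability with the published method is preserved.
- Report next to it, in cm², the baseline low-voltage area and the area excluding it. Label the latter a lower-bound sensitivity figure, because some of that tissue may also have been ablated.

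In section 10.1, state which measures have a pre-to-post percentage change, in agreement with the table.

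The cost is protocol wording, a little extra offline measurement on maps already acquired, some error from registering the two maps, and a companion figure that may be smaller than the main one. No new procedure or patient is needed.

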8.3.2 Proportion of grade 4 occlusion

In this study we will evaluate the proportion of grade 4 occlusion (i.e., contrast stasis) of the 28 mm and 31 mm balloon size POLARx™ FIT cryoablation catheter. Therefore, cine acquisitions of contrast vein occlusions will be analyzed. Occlusion will be categorized by using a previously described scale (1—rapid outflow of contrast medium from the PV to 4—complete contrast retention with no observable leak).²⁴ Two experienced observers blinded to vein outcome will assess recorded venograms.

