3. STUDY DESIGN

3.1 Study design

Investigator-initiated, single-center, open label, prospective, single-arm study evaluating the 31 mm balloon size of the POLARx™ FIT cryoballoon. Before and after complete PVI, a 3-dimensional ultrahigh-density (UHDx) map will be created. The study population will consist of 20 patients undergoing a first PVI with a normal PV anatomy (exclusion of large common ostium or supernumerary veins as determined by a preprocedural CT-scan) in the Erasmus MC, Rotterdam, the Netherlands. Patients will be seen at the outpatient clinic 3 (blanking), 6 and 12 months after the index ablation to assess potential adverse events and recurrence of atrial arrhythmias. After the 1-year visit the study will end for the individual patient. The study flowchart is depicted in Figure 3.1.1.

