4.4 Sample size calculation

With 20 patients we can provide a reliable estimate of the antral lesion area with the 31 mm balloon size of POLARx™ FIT. A recent study by Gunawardene et al. evaluated the antral lesion area in 20 patients who underwent pulmonary vein isolation with a different technique (i.e., pulsed field ablation).²³ The total circumferential antral lesion areas of the left and right sides were 20.5 ± 3.8 and $25.5 \pm 5.7 \text{ cm}^2$, respectively. The precision achieved with 20 patients thus seems adequate to provide a reliable estimate of the antral lesion area. Furthermore, the percentage of technical successful placement of the larger balloon size and the single freeze success percentage are based on the number of PVs (approximately 80 PVs in 20 patients). It is expected that 20 patients will be enrolled in a period of 8 months (approximately 30% enrolment rate of target population), thus an estimated mean inclusion rate of 2.5 patients per month.

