5.1.4 Ablation procedure

After placement of the POLARMAP™ circular mapping catheter in the target PV, the cryoballoon is initially inflated to the standard 28 mm size. The most optimal PV occlusion with the 28 mm balloon size will be achieved and the grade of PV occlusion will be determined using a semi-quantitative grading (1 – rapid outflow of contrast medium from the PV to 4 – complete contrast retention with no observable leak).²⁴ Thereafter, the balloon will increase in size to 31 mm and the most optimal PV occlusion will be achieved. Again, the grade of PV occlusion will be determined using a semi-quantitative grading (grade 0 to 4).²⁴ After optimal PV occlusion with the 31 mm balloon size, a single 3-minutes cryoapplication will be delivered, irrespective of achieving PV isolation. The cryoapplication will be prematurely stopped when the inner balloon temperature is -69°C. If PV isolation is not achieved after the first attempt, subsequent cryoapplications (3 or 4 minutes depending on TTI) are delivered until achieving isolation. The balloon size during subsequent applications can be adjusted according to the preferences of the operator.

The order of PVs will be left superior PV, left inferior PV, right inferior PV, and right superior PV. During cryoablation of the left-sided PVs, a diagnostic catheter will be placed in the right ventricle to provide ventricular pacing in case of a vagal response after cryoablation. During cryoablation of the right-sided PVs, high-output right phrenic nerve stimulation will be performed using a diagnostic catheter in the right subclavian vein or superior vena cava. Diaphragmatic excursion will be checked by a combination of manual palpitation and the use of the Diaphragmatic Movement Sensor (DMS). Whenever the diaphragmatic excursions decrease, cryoablation will be immediately terminated. The following parameters will be noted per cryoapplication: time from ablation till -40 °C, TTI, balloon nadir temperature, thawing time till 0°C.

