10.2 Secondary study parameters

The secondary study parameters are the proportion of grade 4 occlusion and the single shot success rate. Both will be determined per PV and expressed as frequency and percentage (N, %). The difference in the proportion of grade 4 occlusion between the 28 mm and 31 mm balloon size will be compared using the McNemar test for paired nominal data.

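### Section 8.3.2 masks the venogram readers to vein outcome but does not state masking to balloon size, the factor compared in the secondary 28 versus 31 mm grade 4 endpoint

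*Combined protocol and SAP*

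**What the plan says.** Section 8.3.2 plans an offline review of recorded cine at both balloon sizes, on a published four-point scale. On masking it has one sentence: "Two experienced observers blinded to vein outcome will assess recorded venograms".

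The third secondary endpoint in 8.1.2 is "Difference in proportion of grade 4 occlusion with a 28 mm or 31 mm balloon size", at vein level. Section 10.2 says that this difference "will be compared using the McNemar test for paired nominal data".

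The order of sizes is fixed. Under 5.1.4, "the cryoballoon is initially inflated to the standard 28 mm size" and the occlusion is graded. The section continues: "Thereafter, the balloon will increase in size to 31 mm and the most optimal PV occlusion will be achieved". The occlusion is then graded again.

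No other section adds masking of the readers. Section 3.1 describes the trial as follows: "Investigator-initiated, single-center, open label, prospective, single-arm study". The section headed "8.2 Randomisation, blinding, and treatment allocation" contains only N/A. Section 10.2 does not mention the readers.

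**The concern.** Grade 4 is a visual judgement that contrast is fully retained with no visible leak. By choosing an offline read by two partly blinded observers, the plan accepts that knowledge can colour this judgement. The masking it states suits a question in which knowing the vein's outcome could influence the grade. For the 28 versus 31 mm contrast, the knowledge that matters is balloon size, and that is not covered.

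A reader who knew the size could, without intending to, apply the threshold for grade 4 differently at the two sizes. Pairing within the vein gives no protection, because a one-directional tendency goes straight into the discordant pairs that the McNemar test counts. Masking also has to be arranged before grading starts, since a first masked read cannot be recovered afterwards.

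**Working it through.** **Step 1: what is masked, and what is compared.** Section 8.3.2 masks to vein outcome. Sections 8.1.2 and 10.2 compare balloon sizes. Balloon size is set by the operator before the freeze and is not an outcome of the vein, so the stated masking does not include it. Sections 3.1, 5.1.4, 8.2 and 10.2 do not supply it. The open-label label and the N/A under 8.2 describe a single-arm treatment design. They show only that no masking text sits there, not how the cine will be read.

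**Step 2: how size could become known.** The plan does not say how clips are labelled or ordered. Because 28 mm always precedes 31 mm within a vein, a size label, a timestamp or the recording order would each identify the size. The image might too: the diameter ratio is 31/28 = 1.107, and section 6.3 reports an antral shift in balloon position at 31 mm.

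**Step 3: how far the test could move (illustration only).** The plan gives no figure for this endpoint to reproduce. Section 4.4 gives the number of veins as "approximately 80 PVs in 20 patients" (20 × 4 = 80). Assumptions that are not in the plan: one pair per vein, veins independent, exact two-sided McNemar test, alpha 0.05, no true difference.

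Let *c* be the veins graded 4 only at one size and *b* those graded 4 only at the other, with *c* > *b*. Then p = 2 × P(X ≤ *b*), with X binomial(*b* + *c*, 0.5).

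| Opposing veins *b* | Last pair with p ≥ 0.05 | First pair with p < 0.05 | Net excess *c* − *b* | Difference in proportions |
|---|---|---|---|---|
| 0 | 5-0, p = 0.0625 | 6-0, p = 0.0312 | 6 | 6/80 = 7.5 points |
| 2 | 9-2, p = 0.0654 | 10-2, p = 0.0386 | 8 | 8/80 = 10 points |
| 4 | 12-4, p = 0.0768 | 13-4, p = 0.0490 | 9 | 9/80 = 11.25 points |
| 6 | 16-6, p = 0.0525 | 17-6, p = 0.0347 | 11 | 11/80 = 13.75 points |
| 8 | 19-8, p = 0.0522 | 20-8, p = 0.0357 | 12 | 12/80 = 15 points |

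The net excess that first crosses 0.05 is therefore 6 to 12 veins when 0 to 8 veins are discordant the other way.

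This is not a count of clips that must be misread. From a balanced 8-8, regrading seven of the opposing veins gives 8-1, p = 0.039. If all the regraded veins were concordant instead, reaching 20-8 takes twelve.

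**Step 4: the same question by simulation (illustration only).** Suppose that grade 4 is equally likely at both sizes, with rate *r*, and that a share *u* of the 31 mm occlusions truly below grade 4 is read up to grade 4. The spurious difference is *u* × (1 − *r*). The rejection rates below come from 100,000 simulated trials per setting, with within-vein correlation 0 and 0.5. Without bias the exact test rejects in about 3%.

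| *u* | *r* = 80.8%: difference; rejection | *r* = 60%: difference; rejection |
|---|---|---|
| 10% | 1.9 points; about 4% | 4 points; 6-7% |
| 20% | 3.8 points; 6-8% | 8 points; 14-21% |
| 30% | 5.8 points; 12-17% | 12 points; 30-44% |
| 50% | 9.6 points; 33-45% | 20 points; 74-88% |

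The 80.8% is the grade 4 share among 31 mm ablations in the earlier study cited in 6.3, and the 60% is arbitrary. The documents give no value for *u*.

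**The case against.** The strongest reply is that little is at stake. This is the last of three secondary endpoints in a 20-patient, single-arm, largely descriptive study, and no decision is tied to it. The plan already provides offline review, two experienced observers, a published scale and masking to vein outcome. That stands, and it is why the point is minor.

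A second reply is that bias toward 31 mm is presumed. The stated hypothesis concerns lesion size, and the introduction speaks of both benefits and limitations of the larger balloon for occlusion. That also stands: no direction can be taken from the documents.

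A third concerns size. A reader might infer that misreading a small share of all clips would be enough for a false positive. The documents do not support this. The number of regrades depends on which veins they come from, and a clip already at grade 4 cannot be upgraded. If 80.8% applied, about 80 × 0.192 = 15 of the 31 mm clips would be below grade 4, so 6 to 12 upgrades would be some 39% to 78% of them. Downgrading 28 mm clips would widen the pool. Mild bias at that rate hardly moves the test (about 4% against 3%), though at a 60% rate it moves it more.

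Finally, size may be visible on the image. That limits the benefit of masking. It does not justify leaving labels and order unaddressed.

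**Conclusion.** The omission is real: masking to balloon size is not stated anywhere, although size is the factor compared. It is a minor point with a cheap improvement, limited to the secondary 28 versus 31 mm grade 4 comparison. The primary endpoint, antral lesion size from voltage maps, is unaffected.

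A reader might infer from the open-label design and the N/A under 8.2 that the observers will know the size, or that the comparison will favour 31 mm. The documents say neither. They are silent on clip handling, and they give no rate or direction of reader bias.

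The only size that can be put on it is conditional. A net excess of about 6 to 12 veins in one direction first reaches p<0.05, assuming 80 independent veins, an exact two-sided test at 0.05, no true difference and 0 to 8 opposing veins. Veins within a patient may well be correlated, and the plan fixes neither the form of the test nor alpha, so this shows scale and is not a forecast.

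**What to change.** Add to 8.3.2:

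> Cine runs are exported as coded clips with balloon size label, timestamp, sequence and patient identifier removed, and shuffled across veins and sizes. The same two observers grade them masked to vein outcome and, as far as the images allow, to balloon size and order. This offline read is the grade analysed in 10.2; the in-procedure grade (5.1.4) is descriptive.

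The last sentence matters because 5.1.4 and 8.3.2 describe two gradings, and masking helps only if the masked one is analysed. Section 8.3.2 already points that way, and this makes it explicit.

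The cost is a little clip preparation: about 80 × 2 = 160 clips if there is one run per vein and size, and more if several runs are kept. Observers, recordings and patient procedures do not change. Masking may be only partial, because the larger balloon or its antral shift may be visible, and this should be reported as a limitation. The change does not remove the fixed order of sizes or the operator's knowledge of size while optimising each occlusion.
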